8.10.2. Concomitant Procedures

A concomitant procedure is any therapeutic intervention (e.g., surgery/biopsy, physical therapy) or diagnostic assessment (e.g., blood gas measurement, bacterial cultures) performed between Screening and the end of the Post-Treatment Period.

Disallowed Concomitant Procedures

Plasma apheresis is not allowed during the study.

8.11. Treatment Compliance

Compliance with treatment dosing is to be monitored and recorded in the eCRF by Study Center staff.

9. SERIOUS AND NON-SERIOUS ADVERSE EVENT REPORTING

9.1. Sponsor Review of Safety Information

Safety information will be collected, reviewed, and evaluated by the Sponsor or designee in accordance with the applicable Ionis and/or designee Standard Operating Procedures throughout the conduct of the clinical study.

9.2. Regulatory Reporting Requirements

The Sponsor or designee is responsible for regulatory submissions and reporting to the Investigators or designees of SAEs including SUSARs per the ICH guidelines E2A and ICH GCP. Country-specific regulatory requirements will be followed in accordance with local country regulations and guidelines.

Institutional Review Boards/Independent Ethics Committees will be notified of any SAE according to applicable regulations. The DSMB will be notified of any SAE as specified in the DSMB charter.

In addition to the Investigator's or designee's assessment of relatedness, the Sponsor or designee will evaluate the available information and perform an independent assessment of all reported SAEs and determine if there is a reasonable possibility that the Study Drug (ISIS 721744 or placebo) is causally related to a reported SAE and, therefore, meets the definition of an SUSAR. While the Sponsor's independent causality assessment may differ from the Investigator's or designee's assessment, the country-specific regulatory requirements must be followed for expedited reporting of SUSAR to local regulatory authorities.

Appropriate personnel at the Sponsor or designee will unblind SUSARs for the purpose of regulatory reporting. The Sponsor or designee will submit SUSARs to Regulatory Agencies in blinded or unblinded fashion according to local law. The Sponsor or designee will submit SUSARs to Investigators or designees in a blinded fashion.

For the purpose of regulatory reporting of SUSARs, there are not "expected" AEs in this study population. Investigator's Brochure (provided separately) for expected adverse events.

SAEs due to HAE attacks will not be reported on an individual basis in an expedited manner because they are anticipated to occur in the study population independent of the Study Drug (ISIS 721744 or placebo) exposure. The Investigator or designee still has the responsibility to report all SAEs to the Sponsor as described in Section 9.4.1 to Section 9.4.3.5.

HAE attacks will be reported on a HAE attack CRF page and will not be reported as AEs.

The Sponsor or designee and DSMB will monitor these protocol-specified SAEs using the incidence rate of the event in the study compared to the expected incidence rate in a non-Study Drug exposed patient population. If the aggregate analysis indicates that an event is occurring more frequently or at a greater severity than expected, then the event will be reported.

9.3. **Definitions**

9.3.1. Adverse Event

An adverse event (AE) can be any unfavorable and unintended sign (including an abnormal laboratory finding, for example), symptom, or disease temporally associated with the use of medicinal (investigational) product, whether or not the AE is considered related to the medicinal (investigational) product.

An adverse event can therefore be any of the following:

- Any unfavorable and unintended sign (including an abnormal laboratory finding), symptom, or disease temporally associated with the use of a medicinal product, whether or not considered related to the medicinal product
- Any new disease or exacerbation of an existing disease (a worsening in the character, frequency, or severity of a known condition)
- Recurrence of an intermittent medical condition (e.g., headache) not present at Baseline
- Any deterioration in a laboratory value or other clinical test (e.g., ECG, X-ray) that is associated with symptoms or leads to a change in study treatment or concomitant treatment or discontinuation from Study Drug
- Adverse events that are related to a protocol-mandated intervention, including those that occur prior to assignment of study treatment (e.g., screening invasive procedures such as biopsies)

9.3.2. Adverse Drug Reaction and Suspected Unexpected Adverse Drug Reaction Adverse Drug Reaction (ADR)

In the *pre-approval* clinical experience with a new medicinal product or its new usages, particularly as the therapeutic dose(s) may not have been established, ADR is defined as follows:

All noxious and unintended responses to a medicinal product related to any dose should be considered adverse drug reactions.

The phrase "responses to a medicinal product" means that a causal relationship between the medicinal product and the adverse event has been determined by the Sponsor as at least a reasonable possibility, i.e., the relationship cannot be ruled out.

Suspected Unexpected Adverse Drug Reaction

A suspected unexpected ADR is any ADR, the nature or severity of which is not consistent with the applicable product information, e.g., Investigator's Brochure for an unapproved medicinal (investigational) product.

A suspected adverse reaction implies a lesser degree of certainty about causality than an adverse reaction.

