9.4.3. Evaluation of Adverse Events (Serious and Non-Serious)

The Investigator's or designee's opinion of the following should be documented on the Adverse Event Case Report Form:

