9.4.3.1. Relationship to the Study Drug

The event's relationship to the Study Drug (ISIS 721744 or placebo) is characterized by 1 of the following:

- **Related:** There is clear evidence that the event is related to the use of Study Drug (ISIS 721744 or placebo), e.g., confirmation by positive re-challenge test
- **Possible:** The event cannot be explained by the patient's medical condition, concomitant therapy, or other causes, and there is a plausible temporal relationship between the event and Study Drug (ISIS 721744 or placebo) administration
- Unlikely/Remote: An event for which an alternative explanation is more likely (e.g., concomitant medications or ongoing medical conditions) or the temporal relationship to Study Drug (ISIS 721744 or placebo) administration and/or exposure suggests that a causal relationship is unlikely (for reporting purposes, Unlikely/Remote will be grouped together with Not Related)
- **Not Related:** The event can be readily explained by the patient's underlying medical condition, concomitant therapy, or other causes, and therefore, the Investigator or designee believes no relationship exists between the event and Study Drug (ISIS 721744 or placebo)

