4.10.2. Adverse Events (AEs)

AEs will be coded using the MedDRA Version 26.1 or higher.

Treatment-emergent adverse events (TEAEs) will be tabulated and are defined as those AEs that either start or worsen in severity on or after the date/time of first dose of study treatment.

In addition, if severity of an AE changes during the study, a separate AE will be recorded for each severity on the AE CRF. "first" and "second" AE will be identify based on AE start date. AE start date of the second record is AE stop date of first record. AE severity (mild/moderate/severe) are compared between these 2 linked records in a pair for further defining TEAE. Consider 2 cases below:

- Case 1: The first AE record in the pair occurs before first dosing, and the second AE record occurs after first dosing.
 - If the AE severity of the second record is worse than that of the first record, then only the second AE is deemed as a TEAE. Otherwise, neither record is considered as TEAE.
- Case 2: Both AE records in the pair occur after first dosing.
 - If the AE severity on the second record is worse than the severity on the first record, then count both records as treatment-emergent. But, if the severity improves, then only count the first record as treatment-emergent.

All TEAEs identified based on the rules above will be summarized in the event number analysis.

TP-GDO-WW-016-08 CONFIDENTIAL Project Document Version No. 2.0 Effective Date: 26 Nov 19 Project Document Effective Date: 13 Dec 2023 Related to: SOP-GDO-WW-019 Page 39 of 61

The most conservative approach will be used to determine if the event occurs after the treatment. For example, if the onset date or resolution date of an AE is prior to the first study treatment date, it will be considered to have occurred prior to the study period. If the onset or resolution date of an AE is a partial date with only month or year available or complete missing, then the event is assumed to be within the study period unless the year is prior to the year of the first study treatment date, or if in the same year, the month is prior to the month of the first study treatment date.

The incidence of AEs will be summarized by MedDRA PT and SOC for:

- Any TEAEs
- Potentially Related TEAEs. Related is defined as "Related", "Possible", or missing relationship to Study Drug (ISIS 721744 or placebo)

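### The investigator causality scale leaves a gap and is narrower than the protocol's own reasonable-possibility threshold, so the potentially-related TEAE tables can omit events for which a drug cause is a reasonable possibility

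*Combined protocol and SAP*

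**What the plan says.** **The threshold for a drug reaction.** Protocol Section 9.3.2 counts a response as an adverse drug reaction when a causal relationship "has been determined by the Sponsor as at least a reasonable possibility, i.e., the relationship cannot be ruled out". Section 9.2 uses a similar test for serious events: the Sponsor must "determine if there is a reasonable possibility that the Study Drug (ISIS 721744 or placebo) is causally related to a reported SAE". Section 9.2 does not repeat the wording about ruling out, and it covers SAEs only.

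**The scale that is recorded.** Section 9.4.3 gives the recording to the site: "The Investigator's or designee's opinion of the following should be documented on the Adverse Event Case Report Form". Section 9.4.3.1 then offers four categories:

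- *Related* needs clear evidence, with a positive re-challenge as the example.
- *Possible* needs two things at once: "The event cannot be explained by the patient's medical condition, concomitant therapy, or other causes, and there is a plausible temporal relationship".
- *Unlikely/Remote* is "An event for which an alternative explanation is more likely", or one whose timing or exposure points away from the drug. The section adds that "for reporting purposes, Unlikely/Remote will be grouped together with Not Related".
- *Not Related* needs an event readily explained by something else and an investigator who believes there is no link.

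**The tables.** SAP Section 4.10.2 lists a summary of potentially related TEAEs, with the rule "Related is defined as 'Related', 'Possible', or missing relationship to Study Drug". It also lists related TEAEs by severity, and serious and related TEAEs.

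**The concern.** The protocol holds two thresholds for relatedness, and the safety tables use the narrower one. An investigator who thinks the drug may well have caused an event, but who also sees another adequate explanation, cannot choose Possible as it is worded. Such events are plausible here, because on-demand HAE medication, stable androgens and tranexamic acid are allowed alongside study drug (Section 8.10.1).

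Three summaries are at stake: potentially related TEAEs, related TEAEs by severity, and serious and related TEAEs. A reader takes these as covering events for which the drug is a realistic cause. A scale with a gap also invites each site to fill it in its own way, which adds noise to a comparison among groups of 45, 23 and 22 patients.

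**Working it through.** **Step 1: test one event against each category.** Take an event with plausible timing for which the drug and another cause are equally likely.

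| Category (9.4.3.1) | What it requires | Met? |
|---|---|---|
| Related | Clear evidence of causation | No, there is none |
| Possible | No other cause can explain it, and timing fits | No, another cause can explain it |
| Unlikely/Remote | The alternative is more likely, or timing points away from the drug | No, the causes are equal and timing fits |
| Not Related | Readily explained otherwise, and the investigator believes there is no link | No, that belief is not held |

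The event fits nowhere, so the scale is not exhaustive. Yet an equally likely drug cause is a reasonable possibility on any ordinary reading. This result does not depend on taking the final clause of the 9.3.2 definition literally.

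**Step 2: follow the event into the tables.** Under SAP 4.10.2 its fate depends on how the site fills the gap. If it is rated Unlikely/Remote or Not Related, it is left out. If it is rated Possible against the wording, or the field is left blank, it is counted. The text therefore allows omission but does not force it.

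**Step 3: look for a second causality record.** The only Sponsor causality assessment described (Section 9.2) covers SAEs, and nothing in the SAP feeds it into the related-TEAE tables. In the results summary, 33 + 14 + 18 = 65 of 90 patients had any event and 0 + 0 + 1 = 1 had a serious one. For nearly all events, the investigator's category is the only causality rating described.

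**Step 4: bound the size.** No design figure is involved, and the documents give no count of events rated Unlikely/Remote. Assume that the results-summary row for treatment-related problems follows the SAP rule. The patients who could move are those with any event minus those with a related event:

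| Group | Any event | Related | Could move | Range of related rate |
|---|---|---|---|---|
| Every 4 weeks | 33/45 | 19/45 | 33 − 19 = 14 (31%) | 42% to 73% |
| Every 8 weeks | 14/23 | 4/23 | 14 − 4 = 10 (43%) | 17% to 61% |
| Placebo | 18/22 | 6/22 | 18 − 6 = 12 (55%) | 27% to 82% |

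The upper ends are simply the any-event rates, and the pools include events that were plainly unrelated. The bound covers only the row for patients with at least one related event. Severity and preferred-term counts could also change within patients who already have a related event.

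**Step 5: check the direction between arms.** The reported every-4-weeks minus placebo difference is 42.2% − 27.3% = 14.9 points. For illustration only, suppose the same share of each pool moved:

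- 10% moves: (42.2 + 3.1) − (27.3 + 5.5) = about 12.6 points.
- 30% moves: (42.2 + 9.3) − (27.3 + 16.4) = about 7.9 points.
- All move: 73.3 − 81.8 = −8.5 points.

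For every 8 weeks minus placebo, the difference goes from 17.4 − 27.3 = −9.9 points to (17.4 + 13.0) − (27.3 + 16.4) = about −13.2 points at 30%. Under equal shares, placebo rises most. Unequal shares could move either comparison the other way: if only the every-4-weeks pool moved, its difference would be 73.3 − 27.3 = 46.1 points from unrounded fractions. The documents do not fix the sign.

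**Step 6: compare the pause criteria.** Section 8.8.2 relies on the treating investigator's relatedness judgement but does not cite 9.4.3.1. Its criterion for deaths uses grades of probable and definite relationship, which the 9.4.3.1 scale does not contain.

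**The case against.** The strongest reply is that the two thresholds belong to different assessors. Section 9.3.2 describes a Sponsor determination, while the tables report the investigator's opinion. Section 9.2 accepts that the two may differ. Neither document calls the related-TEAE tables adverse-drug-reaction tables. This stands: an event left out of those tables is not thereby shown to meet the 9.3.2 definition, and a reader who infers that the tables do omit protocol-defined drug reactions goes further than the text allows. What survives is that the tables are presented as potentially related events, and the scale behind them has no place for some events that are.

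A reader might also infer that the tables understate the harm of the drug. The documents do not support that either. The wording does not push the ambiguous event into the unrelated group, a blank field counts as related, and placebo could rise most.

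A third reply is that the safety assessment does not rest on these tables. Any-TEAE, TEAE-by-severity and SAE summaries and the full AE listing do not use the relationship field. The injection-site (LCRIS), flu-like and bleeding summaries have their own definitions. That stands too, and it limits the consequence.

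Finally, if the ruling-out clause in 9.3.2 is read literally, many Unlikely/Remote events would qualify as well. That reading is open to argument, and the point does not need it.

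**Conclusion.** The point holds as a defect in a classification rule. The 9.4.3.1 scale is not exhaustive and is narrower than reasonable possibility. Because SAP 4.10.2 relies on it alone, the three related-TEAE summaries can omit events for which a drug cause is a reasonable possibility, and sites may rate like events differently.

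No omitted event is shown. The size lies somewhere within 0 to 14 of 45, 0 to 10 of 23 and 0 to 12 of 22 patients, provided the results-summary row follows the SAP rule. The documents do not locate it within those ranges or give the direction between arms; the 10% and 30% shares above are assumptions. Efficacy analyses and the summaries that do not depend on causality are unaffected. It is worth correcting because following the rule as written can misclassify events and the correction is cheap.

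**What to change.** 1. **Protocol 9.4.3.1 and CRF guidance.** Reword Possible as plausible timing with a causal relationship that is at least a reasonable possibility, even if another cause could also explain the event. Keep Unlikely/Remote for events where the alternative is more likely or the timing argues against the drug. Reconcile the final clause of the 9.3.2 definition with this, so that both sections state one threshold.
2. **SAP 4.10.2, for data recorded on the present wording.** Add one sensitivity row counting every TEAE not rated Not Related (Related, Possible, Unlikely/Remote or missing). Label it an upper bound, because it includes events judged more likely due to another cause. It cannot recover an ambiguous event that a site rated Not Related. It needs the four categories to be stored separately, which 9.4.3.1 implies, since the grouping there is for reporting.
3. **Protocol 8.8.2.** Reconcile its relatedness terms with the 9.4.3.1 scale. The pause rule itself is not in question here.

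The results summary says the study ended in November 2023, so item 2 is the part that can still help readers of this trial. The cost is one definition and one table row on data already recorded. The downside is higher related-TEAE percentages in all arms, possibly most on placebo.

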9.3.3. Serious Adverse Event (SAE)

A SAE is any adverse event that in the view of either the Investigator or designee or Sponsor, meets any of the following criteria:

- Results in death
- Is life threatening: that is, poses an immediate risk of death at the time of the event An AE or suspected adverse reaction is considered "life-threatening" if, in the view of either the Investigator or designee or Sponsor, its occurrence places the patient at immediate risk of death. It does not include an AE or suspected adverse reaction that, had it occurred in a more severe form, might have caused death
- Requires inpatient hospitalization or prolongation of existing hospitalization Hospitalization is defined as an admission of greater than 24 hours to a medical facility and does not always qualify as an AE
- Results in a persistent or significant incapacity or substantial disruption of the ability to conduct normal life functions
- Results in a congenital anomaly or birth defect in the offspring of the patient (whether the patient is male or female)
- Important medical events that may not result in death, are not life-threatening, or do not require hospitalization may also be considered serious when, based upon appropriate medical judgment, they may jeopardize the patient and may require medical or surgical intervention to prevent one of the outcomes listed in this definition. Examples of such medical events include allergic bronchospasm requiring intensive treatment in an ER or at home, blood dyscrasias or convulsions that do not result in inpatient hospitalization, or the development of drug dependency or drug abuse.

The terms "severe" and "serious" are not synonymous. Severity refers to the intensity of an adverse event (e.g., rated as mild, moderate, or severe, or according to National Cancer Institute Common Terminology Criteria for Adverse Events [NCI CTCAE]; OR Toxicity Grading Scale for Healthy Adult and Adolescent Volunteers Enrolled in Preventive Vaccine Clinical Trials; the event itself may be of relatively minor medical significance (such as severe headache without any further findings).

Severity and seriousness need to be independently assessed for each adverse event recorded on the eCRF.

9.3.4. Adverse Event of Special Interest (AESI)

For the purpose of this study, severe reductions in PLT count < 50,000/mm³ accompanied by a MB event or CRNMB event, or PLT count of < 25,000/mm³ independent of a MB or CRNMB event, are considered as AEs of special interest (AESIs) and are subject to 15-day expedited reporting by the Sponsor to the regulatory agencies.

Amendment 2 12 July 2022

Adverse events of special interest are required to be reported by the Investigator or designee to the Sponsor immediately, within 24 hours of the Study Center's first knowledge of the event, for expedited reporting to Regulatory Authorities.

9.4. Monitoring and Recording Adverse Events

Any pre-existing conditions or signs and/or symptoms present in a patient prior to the start of the study (i.e., before informed consent and, as applicable, assent) should be recorded as Medical History and not recorded as AEs unless the pre-existing condition worsened. The Investigator or designee should always group signs and symptoms into a single term that constitutes a **single unifying diagnosis** if possible. Before a diagnosis is confirmed, all symptoms should be reported as separate AEs.

9.4.1. Serious Adverse Events (SAE)

In the interest of patient safety, and in order to fulfill regulatory requirements, all SAEs (regardless of their relationship to Study Drug) should be reported to the Sponsor or designee within 24 hours of the Study Center's first knowledge of the event. The collection of SAEs will begin after the patient signs the ICF and will stop at the end of the patient's Post-Treatment Period, which is defined as completion of the Week 13 Visit of the Post-Treatment Period, or patient has Day 1/Week 1 in the OLE study. Serious adverse events should be reported using electronic SAE submission (via Electronic Data Capture [EDC]) whenever possible. In situations where electronic SAE submission is unavailable, a paper Initial Serious Adverse Event Form should be completed, and a copy should be faxed or emailed to the Sponsor or designee. The SAE reporting instructions, including the fax number and email address, can be found in the Investigator Site File for the study.

Detailed information should be actively sought and included as Follow-Up as soon as additional information becomes available. All SAEs will be followed until resolution. Serious adverse events that remain ongoing past the patient's last protocol-specified visit will be evaluated by the Investigator or designee and Sponsor. If the Investigator or designee and Sponsor agree that the patient's condition is unlikely to resolve, the Investigator or designee and Sponsor will determine the follow-up requirement.

